10. APPENDICES

Section	Appendix
RAP Section 5 : General Considerations for Data Analyses & Data Handling Conventions	
Section 10.1	Appendix 1: Protocol Deviation Management
Section 10.2	Appendix 2: Time & Events
Section 10.3	Appendix 3: Assessment Windows & Visit Slotting
Section 10.4	Appendix 4: Treatment Phases
Section 10.5	Appendix 5: Data Display Standards & Handling Conventions
Section 10.6	Appendix 6: Derived and Transformed Data
Section 10.7	Appendix 7: Premature Withdrawals & Handling of Missing Data
Section 10.8	Appendix 8: Population Pharmacokinetic Analyses
Other RAP Appendices	
Section 10.9	Appendix 9: Abbreviations & Trade Marks
Section 10.10	Appendix 10: List of Data Displays
Section 10.11	Appendix 11: Example Mock Shells for Data Displays

10.1. Appendix 1: Protocol Deviation Management

- As detailed in Section 4.1 protocol deviations will be tracked by the study team throughout the conduct of the study in accordance with the Protocol Deviation Management Plan (PDMP) and important protocol deviations (including deviations related to study inclusion/exclusion criteria, conduct of the trial, patient management or patient assessment) will be listed and summarised.
- A Per Protocol Population will not be defined for this study. However if there are subjects with protocol deviations that may potentially impact either the PK or the PD endpoints, exploratory sensitivity analyses may be considered (See Section 7). Any additional sensitivity analyses will be documented in the CSR.

10.2. Appendix 2: Time & Events**10.2.1. Time & Events Table Pharmacokinetic/Pharmacodynamic Phase (Part A)**

Procedure	Pre-Screen ¹	Screening	Treatment Period				Exit Visit ³	Follow-up		Early Withdrawal
			2	3	4	5		6	7	
Visit Number	0	1	2	3	4	5	6	7	8 ⁸	
Week of Study (visit window \pm 3 days, \pm 1 day Visit 5))	Prior to or same day as Visit 1	(up to 14 days prior to Visit 2)	0	4	8	9	12	16	20	
Subject Screen										
Informed consent	X									
Inclusion and exclusion criteria		X	X							
Demography	X									
Medical history, including bronchodilator reversibility history ⁴		X								
Past and current medical conditions		X								
Asthma exacerbation history		X								
Safety Assessments										
Concomitant medications	X	X	X	X	X	X	X	X	X	X
Hematology (including eosinophils)		X	X	X	X	X	X	X	X	X
Clinical Chemistry		X		X	X		X		X	X
12-lead ECG		X		X			X			X
Vital signs		X	X	X	X	X	X	X	X	X
Bodyweight			X							
Brief physical examination		X								
Adverse events		X	X	X	X	X	X	X	X	X
Cardiovascular events		X	X	X	X	X	X	X	X	X
Liver events		X	X	X	X	X	X	X	X	X
Laboratory Assessments										
Urinalysis		X							X	X
Pregnancy Test		U	U ⁵	U ⁵	U ⁵		U	U	U	U
HBsAg and hepatitis C antibody		X ⁶								
Serum IgE (total and specific)			X ⁵							
PK blood sample				X ⁵	X ⁵	X	X	X	X	X

Procedure	Pre-Screen ¹	Screening	Treatment Period				Exit Visit ³	Follow-up		Early Withdrawal
			2	3	4	5		6	7	
Visit Number	0	1	2	3	4	5	6	7	8 ⁸	
Week of Study (visit window \pm 3 days, \pm 1 day Visit 5))	Prior to or same day as Visit 1	(up to 14 days prior to Visit 2)	0	4	8	9	12	16	20	
IL5 serum sample			X ⁵				X			
Blood sample for immunogenicity ^{2,7}			X ⁵					X	X ²	X
Outcomes Assessments										
FEV1		X	X	X	X		X	X	X	X
ACQ-7			X	X	X		X	X	X	X
C-ACT			X	X	X		X	X	X	X
Assessment of exacerbation	X	X	X	X	X	X	X	X	X	X
Investigational Product										
Mepolizumab SC dose administered			X	X	X					
Study Administration										
Email to GSK Operational Lead	X	X	X	X	X	X	X	X	X	X
Complete eCRF	X	X	X	X	X	X	X	X	X	X

1. Pre-screen must be completed prior to or on the same day as Screen Visit.
2. For subjects who had a positive anti-mepolizumab antibody response at the 12 week post-last-dose follow-up assessment (Visit 8) (or last study visit at which immunogenicity was assessed if the Follow-up (Visit 8) immunogenicity sample is not available) an attempt will be made to obtain a serum sample for anti-mepolizumab antibodies at least 4 months after the last dose of study drug in Part A or upon completion of Part A, whichever is later.
3. Exit visit should be performed as close as possible to the planned week 12 visit date.
4. Therapy history to include a detailed review of prior biologics received for treatment of asthma, including prior investigational anti-IL5 or anti-IL13 preparations.
5. During the treatment period, all lab samples and procedures should be obtained prior to study treatment administration.
6. A positive Hepatitis B Surface Antigen and Hepatitis C antibody is exclusionary
7. This immunogenicity sample must always be collected 12 weeks (\pm 7 days) post-last-dose of study treatment; therefore, for subjects who withdraw from study treatment early, this sample must be collected 12 weeks (\pm 7 days) after their confirmed last dose of study treatment (i.e., prior to Visit 8). In the event that this sample collection date coincides with an Early Withdrawal Visit, only one immunogenicity sample should be collected.
8. Visit 8 to be performed 12 weeks post last dose. For subjects continuing into the long-term extension phase Part B, Visit 9 should be conducted on the same day as Visit 8 once all of the visit 8 assessments have been completed. Assessments performed at Visit 8 that are also listed for Visit 9 should not be duplicated if Visit 8 and Visit 9 are performed on the same day.

10.2.2. Time and Events Table Long-Term Safety / Pharmacodynamic Phase (Part B)

Procedure	Eligibility Check / First Dose	Treatment Period												Exit Visit	Follow-up	Early Withdrawal
		9	10	11	12	13	14	15	16	17	18	19	20			
Visit	9	10	11	12	13	14	15	16	17	18	19	20	21	22	23	
Week of Study (visit window \pm 5 days)	20	24	28	32	36	40	44	48	52	56	60	64	68	72	80	
Subject Screen																
Informed consent	X ¹															
Inclusion and exclusion criteria	X ¹															
Safety Assessments																
Concomitant medications	X	X	X	X	X	X	X	X	X	X	X	X	X	X	X	X
Hematology (including eosinophils) ²	X			X			X			X			X	X	X	
Clinical Chemistry ²	X			X			X			X			X	X	X	
12-lead ECG														X	X	
Vital signs	X	X	X	X	X	X	X	X	X	X	X	X	X	X	X	
Bodyweight	X	X ¹	X ¹	X ¹	X ¹	X ¹	X ¹	X ¹	X ¹	X ¹	X ¹	X ¹	X ¹			
Adverse events	X	X	X	X	X	X	X	X	X	X	X	X	X	X	X	
Cardiovascular events	X	X	X	X	X	X	X	X	X	X	X	X	X	X	X	
Liver events	X	X	X	X	X	X	X	X	X	X	X	X	X	X	X	
Laboratory Assessments²																
Urinalysis	X ¹					X								X	X	
Pregnancy Test	U	U	U	U	U	U	U	U	U	U	U	U	U	U	U	
Blood sample for immunogenicity ²							X						X	X	X	
Outcomes Assessments																
FEV1	X ¹			X			X			X			X	X	X	
ACQ-7	X ¹			X			X			X			X	X	X	
C-ACT	X ¹			X			X			X			X	X	X	
Assessment of exacerbation	X	X	X	X	X	X	X	X	X	X	X	X	X	X	X	

Procedure	Eligibility Check / First Dose	Treatment Period												Exit Visit	Follow- up	Early Withdrawal
		10	11	12	13	14	15	16	17	18	19	20	21			
Visit	9													22	23	
Week of Study (visit window \pm 5 days)	20	24	28	32	36	40	44	48	52	56	60	64	68	72	80	
Investigational Product																
Mepolizumab SC dose administered	X	X	X	X	X	X	X	X	X	X	X	X	X			
Study Administration																
Email to GSK Operational Lead	X	X	X	X	X	X	X	X	X	X	X	X	X	X	X	X
Complete eCRF	X	X	X	X	X	X	X	X	X	X	X	X	X	X	X	X

 1. Bodyweight will be measured at Visit 9 and at each visit until such time as the subject reaches 40kg in weight. Subjects with bodyweight \geq40Kg at Visit 9 will not be weighed again during Part B. 2. All laboratory samples should be collected prior to the administration of study medication 																

10.3. Appendix 3: Assessment Windows & Visit Slotting

10.3.1. Study Part (Part A and Part B)

Data will be collected across two study parts (Part A and Part B) within a single study database. Data will be attributed to an individual study part according to the time of occurrence/assessment relative to specific visits.

Data points collected at scheduled clinic visits will be attributed to the correct study part utilising the collected visit label.

Spontaneous events (such as adverse events, exacerbations and unscheduled visits) will be attributed to an individual study part as follows:

Study Part	Definition
Part A	Visit 0 (Pre-screening) visit date \leq Date & time \leq Visit 8 (Week 20) visit date
Part B	Visit 9 (Week 20) visit date $<$ Date & time \leq Visit 23 (Week 80) visit date
Note: Visit 8 and Visit 9 will be performed on the same date	

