6.8. Treatment after the Completion of Part A and Part B

The investigator is responsible for ensuring that consideration has been given to the post-study care of the patient's medical condition whether or not GSK is providing specific continuing study treatment under Part B of this study.

At the end of Part A, a benefit/risk assessment will be performed by the Investigator and if this assessment supports continued therapy with mepolizumab the subject will be offered the opportunity to enrol in Part B following the Part A Follow-up visit (Visit 8). Part B will continue for 52 weeks of additional mepolizumab treatment.

At the end of Part B, when feasible, subjects will transition to a long term access program. At the end of the Treatment Phase of Part B, subjects that are not able to transition to the long term access program will return to usual care and will be prescribed appropriate alternative asthma therapy, as required.

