Bodyweight	X	X ¹	X ¹	X ¹	X ¹	X ¹	X ¹	X ¹	X ¹	X ¹	X ¹	X ¹	X ¹				
Adverse events	X	X	X	X	X	X	X	X	X	X	X	X	X	X	X	X	
Cardiovascular events	X	X	X	X	X	X	X	X	X	X	X	X	X	X	X	X	
Liver events	X	X	X	X	X	X	X	X	X	X	X	X	X	X	X	X	
Laboratory Assessments²																	
Urinalysis	X ¹					X								X		X	
Pregnancy Test	U	U	U	U	U	U	U	U	U	U	U	U	U	U	U	U	
Blood sample for immunogenicity ²							X						X		X	X	
Outcomes Assessments																	
FEV1	X ¹			X			X			X			X	X	X	X	
ACQ-7	X ¹			X			X			X			X	X	X	X	
C-ACT	X ¹			X			X			X			X	X	X	X	

Procedure	Eligibility Check / First Dose	Treatment Period												Exit Visit	Follow-up ³	Early Withdrawal
Visit	9	10	11	12	13	14	15	16	17	18	19	20	21	22	23	
Week of Study (visit window \pm 5 days)	20	24	28	32	36	40	44	48	52	56	60	64	68	72	80	
Assessment of exacerbation	X	X	X	X	X	X	X	X	X	X	X	X	X	X	X	X
Investigational Product																
Mepolizumab SC dose administered	X	X	X	X	X	X	X	X	X	X	X	X	X			
Study Administration																
Email to GSK Operational Lead	X	X	X	X	X	X	X	X	X	X	X	X	X	X	X	X
Complete eCRF	X	X	X	X	X	X	X	X	X	X	X	X	X	X	X	X

1. Bodyweight will be measured at Visit 9 and at each visit until such time as the subject reaches 40kg in weight. Subjects with bodyweight \geq 40Kg at Visit 9 will not be weighed again during Part B.
2. All laboratory samples should be collected prior to the administration of study medication
3. The 12-week post-dose follow-up visit (Visit 23) is not required for subjects transitioning to the long-term access program.

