10.4. Appendix 4: Treatment Phases

10.4.1. Treatment Phases (Adverse Events)

Adverse events will be classified according to time of occurrence relative to the first and last dose of mepolizumab within specific study parts.

Treatment Phase	Definition
Pre-Treatment	AE Onset Date & time < First Part A dose of mepolizumab If mepolizumab treatment is never started then all AEs will be classified as pre-treatment.
On-Treatment (Part A)	First Part A dose of mepolizumab ≤ AE Onset Date & time ≤ Last Part A dose of mepolizumab + 28 days If an AE start date is missing or partial then the AE will be considered on-treatment unless there is evidence to the contrary (e.g. month/year of onset date is present and is earlier than the month/year of First Part A dose of mepolizumab).
Post-treatment (Part A)	For subjects entering Part B: Last Part A dose of mepolizumab + 28 days < AE Onset Date & time < First dose of Part B mepolizumab For subjects not entering Part B: Last Part A dose of mepolizumab + 28 days < AE Onset Date & time ≤ Visit 8 (Week 20) visit date
On-Treatment (Part B)	First dose of Part B mepolizumab ≤ AE Onset Date & time ≤ Last Part B dose of mepolizumab + 28 days If an AE start date is missing or partial then the AE will be considered on-treatment unless there is evidence to the contrary (e.g. month/year of onset date is present and is earlier than the month/year of First Part B dose of mepolizumab).
Post-treatment (Part B)	AE Onset Date & time > Last Part B dose of mepolizumab + 28 days
Onset Time Since 1 st Dose (Days)*	If Treatment Start Date > AE Onset Date = AE Onset Date - First Part A dose of mepolizumab If Treatment Start Date ≤ AE Onset Date = AE Onset Date - First Part A dose of mepolizumab + 1 If Treatment Start Date or AE Onset Date is missing = missing.
Duration (Days)	AE Resolution Date – AE Onset Date + 1
Drug-related	If relationship is marked 'YES' on Inform/eCRF OR value is missing.
* Note: will be derived as time since 1 st dose of mepolizumab utilising the First Part A dose of mepolizumab for both study parts A and B	

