10.4.2. Treatment Phases (Exacerbations)

Exacerbation data will be classified according to time of occurrence/assessment relative to the first and last dose of mepolizumab and the participation of subjects within to specific study parts (as dictated by attendance dates of specific visits).

Treatment Phase	Definition
Pre-Treatment	Exacerbation Onset Date & time < First Part A dose of mepolizumab If mepolizumab treatment is never started then all exacerbations will be classified as pre-treatment.
On-Treatment (Part A)	Subjects completing Part A: First Part A dose of mepolizumab ≤ Exacerbation Onset Date & time ≤ Visit 6 (Week 12) visit date Subjects discontinuing study treatment/withdrawing early from Part A: First Part A dose of mepolizumab ≤ Exacerbation Onset Date & time ≤ Earliest of (1) Last Part A dose of mepolizumab + 28 days or (2) Early Withdrawal visit date
Post-treatment (Part A)	Subjects completing Part A and entering Part B: Visit 6 (Week 12) visit date < Exacerbation Onset Date & time < First dose of Part B mepolizumab Subjects completing Part A and not entering Part B: Visit 6 (Week 12) visit date < Exacerbation Onset Date & time ≤ Visit 8 (Week 20) visit date Subjects discontinuing study treatment/withdrawing early from Part A: Earliest of (1) Last Part A dose of mepolizumab + 28 days or (2) Early Withdrawal visit date < Exacerbation Onset Date & time ≤ Visit 8 (Week 20) visit date
On-Treatment (Part B)	Subjects completing Part B: First Part B dose of mepolizumab ≤ Exacerbation Onset Date & time ≤ Visit 22 (Week 72) visit date Subjects discontinuing study treatment/withdrawing early from Part B: First Part B dose of mepolizumab ≤ Exacerbation Onset Date & time ≤ Earliest of (1) Last Part B dose of mepolizumab + 28 days or (2) Early Withdrawal visit date
Post-treatment (Part B)	Subjects completing Part B: Exacerbation Onset Date & time > Visit 22 (Week 72) visit date Subjects discontinuing study treatment/withdrawing early from Part B: Exacerbation Onset Date & time > Earliest of (1) Last Part B dose of mepolizumab + 28 days or (2) Early Withdrawal visit date

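### SAP 10.3.1 ends Part B at a visit that transitioning subjects do not have, and cuts Part A from Part B at a different point from 10.4.1 and 10.4.2

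*SAP*

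**What the plan says.** SAP 10.3.1 places data from scheduled visits by visit label. For the rest it gives a date rule: "Spontaneous events (such as adverse events, exacerbations and unscheduled visits) will be attributed to an individual study part as follows". Part A runs from the pre-screening date up to and including the Visit 8 date. Part B runs from strictly after the Visit 9 date up to the "Visit 23 (Week 80) visit date". A footnote adds: "Note: Visit 8 and Visit 9 will be performed on the same date". No alternative end date is given.

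Two later sections define treatment phases. For adverse events (10.4.1): "Adverse events will be classified according to time of occurrence relative to the first and last dose of mepolizumab within specific study parts". For exacerbations (10.4.2): "Exacerbation data will be classified according to time of occurrence/assessment relative to the first and last dose of mepolizumab", together with attendance dates of specific visits. In both, the Part A post-treatment phase of a subject who enters Part B stops just before the first Part B dose. On-Treatment (Part B) starts at that dose, by date and time. Neither section uses Visit 23, and their Part B post-treatment phases have no upper limit.

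The current protocol (Table 4, footnote 3) says: "The 12-week post-dose follow-up visit (Visit 23) is not required for subjects transitioning to the long-term access program". Protocol 6.8 makes transition the intended route: "At the end of Part B, when feasible, subjects will transition to a long term access program". Protocol 5.6 counts these subjects as completers once the Part B treatment phase is done. The SAP states that it is based on Amendment 4, and its Section 2.3 still gives Part B subjects a follow-up visit 12 weeks after the last dose.

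**The concern.** Every by-part display needs one rule that puts each event in exactly one part. Section 10.3.1 does not do this for a subject without Visit 23, and on the Visit 8/9 day it disagrees with the sections that define treatment phases. No statement in the SAP says which rule takes precedence. Section 10.3.1 names adverse events and exacerbations explicitly, and 10.4.1 works within study parts that 10.3.1 defines, so a programmer could defend either order.

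Adverse event incidence is a Part B primary endpoint. What is at stake is agreement between displays. If phase-labelled tables follow 10.4.1 and part-only displays follow 10.3.1, the same event can be counted in a Part B on-treatment table and be absent from the Part B event listing. The choice would also be made in programming rather than in the plan.

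**Working it through.** There is no sample size, power or event figure to reproduce. The check is to apply the three rules literally to the same events.

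**Inputs**
- SAP 10.3.1: Part A if onset ≤ Visit 8 date; Part B if Visit 9 date < onset ≤ Visit 23 date; Visit 8 date = Visit 9 date.
- SAP 10.4.1: Post-treatment (Part A) if last Part A dose + 28 days < onset < first Part B dose; On-Treatment (Part B) if first Part B dose ≤ onset ≤ last Part B dose + 28 days.
- SAP 10.4.2: the same start for On-Treatment (Part B); it ends at Visit 22 for completers.
- Protocol Table 4: Part B doses at Visits 9 to 21 (Weeks 20 to 68), Visit 22 at Week 72, Visit 23 at Week 80.
- Illustrative assumption: first Part B dose at 11:00 on the Visit 8/9 day. The conflict does not depend on the hour.

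**Classification, with visit dates read as calendar dates**

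| Event | 10.3.1, Visit 23 done | 10.3.1, no Visit 23 | 10.4.1 and 10.4.2 |
|---|---|---|---|
| Visit 8/9 day, 09:00 (pre-dose) | Part A | Part A | Post-treatment (Part A) |
| Visit 8/9 day, 15:00 (post-dose) | Part A | Part A | On-Treatment (Part B) |
| Week 30 | Part B | neither part | On-Treatment (Part B) |
| Week 71 | Part B | neither part | On-Treatment (Part B) |

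**End of Part B.** With no Visit 23 date the Part B inequality cannot be satisfied at any week. Taken literally, the gap covers a transitioning subject's whole Part B (72 − 20 = 52 weeks), not only Weeks 72 to 80.

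**Boundary.** The second row is the conflict. Reading the visit date as midnight does not remove it: the 15:00 event then agrees (with Visit 23 done), but the 09:00 pre-dose event becomes Part B under 10.3.1 while remaining Post-treatment (Part A) under 10.4.1 and 10.4.2.

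**Size**
- Dosing days: (68 − 20)/4 + 1 = 13, so the boundary touches 1 of 13 (7.7%).
- Days from Week 20 to Week 72: 52 × 7 + 1 = 365, so one day of 365.
- Subjects without Visit 23 through transition: 28 × f, where 28 is the planned number treated in Part A (an assumed upper bound for Part B entry) and f, the share transitioning, is not stated. The range is 0 to 28.

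**Displays.** On the SAP's display list, Part B Tables 2.32, 3.55, 3.66, 3.71–3.74, 3.92 and 3.93 and Listing 58 are examples titled by part with no phase. Their Part A counterparts (Tables 2.19, 3.2, 3.13, 3.18–3.21, 3.39 and 3.40, Listing 12) are in the same position. Listing 56, a Part B exacerbation listing, does point to 10.4.2, but its note asks for events in Part A.

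**The case against.** The strongest reply to the Visit 23 point is that it is version lag. Under Amendment 4 every Part B subject was due a Week 80 visit, so the end date was coherent when written, and an updated SAP may exist that is not among the documents. That explains the cause, but the current protocol and this SAP still do not fit together. A subject lost to follow-up lacks the date under either amendment.

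It can also be said that withdrawn subjects are covered: Protocol 5.5 uses data collected up to withdrawal, and SAP 10.7.1 lists all their available data. Both provisions stand, but they say that the data are used, not which part they belong to. Nor do they cover transitioning subjects, who are completers.

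A third reply is that 10.4.1 and 10.4.2 plainly govern. For phase-labelled tables that is right. For part-only displays nothing says so, and unscheduled visits fall under 10.3.1 alone.

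A reader might infer that Part B on-treatment adverse event incidence is biased, or that events are lost. The documents do not support either. On-treatment tables follow 10.4.1, which does not use Visit 23. Under the calendar-date reading, a post-dose Visit 9 event is filed under Part A rather than dropped. An injection reaction that day would still appear in the on-treatment special-interest tables. Several part-only tables defer to shells that are not in the documents and may already split by phase.

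**Conclusion.** Both defects hold on current text. Section 10.3.1 cannot place Part B events for a subject with no Visit 23, and its boundary contradicts 10.4.1 and 10.4.2 on the Visit 8/9 day. The boundary conflict is internal to the SAP and does not depend on Amendment 5.

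The consequence is limited to possible disagreement between part-only and phase-labelled displays. It rests on two assumptions: that part-only displays would be programmed from 10.3.1, and that their shells do not already split by phase. Neither can be checked. The transition share is not stated, so the number of subjects affected is unknown, and no change in incidence can be computed. Severity is minor to moderate: a wrong rule worth correcting, with no demonstrated effect on the Part B primary endpoint.

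**What to change.** In SAP 10.3.1:
- Set the Part A/Part B boundary at the date and time of the first Part B dose. For a subject who does not enter Part B, end Part A at Visit 8 or last contact.
- End Part B at Visit 23 or, if it is not done, at the subject's last Part B contact.
- State that the 10.4.1 and 10.4.2 boundaries govern study-part attribution in all displays, with or without a phase label.
- State how a Visit 9-day event with a full date but no onset time is assigned. The existing default in 10.4.1 does not reach it: "If an AE start date is missing or partial then the AE will be considered on-treatment unless there is evidence to the contrary".

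Correct the Listing 56 note to Part B, and align the SAP with Amendment 5 before the Part B database lock.

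The cost is wording and programming. Protocol 6.3 already has dose date and time reported in the eCRF. The documents do not confirm that event onset time is collected, which is why the no-time rule is needed.

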10.3.2. Part A Data Cut Date

When reporting study Part A, a data cut date will be applied to all data collected within the Case Report Form (CRF) prior to SDTM conversion. This cut date subset the data to only those assessments/visits prior to the last subject completing the Visit 8 (Week 20) visit date (LSLV Part A).

All external vendor data (e.g. Labs, ECGs, Immunogenicity) will not be possible to subset and therefore data will be present within the SDTM datasets past this data cut date.

When creating ADaM datasets all dates beyond this applied data cut date will be removed and will be documented clearly within the ADaM dataset metadata.

